**Secondary outcomes:**

The secondary outcomes will be the four criteria outlined by Bahadoran et al. as indicators of a well-written abstract:

- a) Informativeness
- b) Accuracy
- c) Attractiveness
- d) Conciseness.

The extent to which participants perceive these criteria to be fulfilled will be quantified on a 4-point Likert scale, e.g. very little informative, little informative, informative, very informative. For data analysis, the data will be dichotomized. For instance, the statements "very little informative" and "little informative" will be summarized in the category "non-informative," while the statements "informative" and "very informative" will be summarized in the category "informative."

Additionally, the time needed to read the abstract will be quantified. The time interval is defined as the period between the participant clicking on the link in the email and clicking on the „Continue" button to proceed to the survey. This time will be automatically recorded by SoSci Survey.

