**Secondary:**

The secondary objective will be to assess the perception of an abstract based on the four indicators of a well-written abstract, outlined by Bahadoran et al. These indicators state that abstracts should be: a) informative, b) accurate, c) attractive, and d) concise.

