***Intervention:***

In this study, we will attempt to emulate the reading process observed in PubMed. When searching PubMed, researchers are initially presented with an overview of the references identified. After clicking on the title, the corresponding abstract appears. For full-text access, researchers must actively follow a separate link to the journal page.

In this RCT, participants are randomly assigned to two groups (those receiving a long abstract vs. those receiving a short abstract). Both groups receive the same cover letter by e-mail explaining the purpose of the study, the use of the data, measures to ensure anonymity of participation and a link for participation. When participants click on the link, they automatically confirm their participation in the study.

The link will direct participants to SoSci Survey, an online survey tool. Those in the group receiving the long abstract will see an abstract with a length of 771 words (PMID: 37955353). Those in the group receiving the short abstract will see an abstract with a length of 277 words (PMID: 37942649). Both abstracts are structured and pertain to the same review by Soderberg et al. entitled "Percutaneous nephrolithotomy vs. retrograde intrarenal surgery for renal stones". This review was published once in the Cochrane Database of Systematic Reviews and once in the journal BJU International.

The design of the abstract presented is similar to that of PubMed, but no title or authors will be indicated. After reading the abstract, participants must actively click the "Continue" button to proceed.

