***Outcomes:***

**Primary outcome:**

The primary outcome of this RCT will be the trial participation, which is defined as the proportion of participants who read the abstract and then clicked on the "Continue" button. This will be quantified by dividing the number of participants who read the abstract and proceeded to complete the survey by the total number of individuals who clicked on the link in the email. Information will be electronically captured in SoSci survey.

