**Sample size:**

Assuming an 80% trial participation in the control group, a two-sided significance level of 5% ( $\alpha = 0.05$ ), and a power of 90% ( $\beta=10\%$ ), 558 participants (279 per group) are needed to detect a relative difference in trial participation of 15% (80% vs. 68%). The sample size calculation was carried out using the PROC POWER function in SAS. Given an expected response of 9.6%, the sample size was estimated to be 5813. Additionally, expecting an approximately 5% exclusion due to study types other than SR^13 or duplicate email addresses, the sample size was increased to 6103. To achieve this, a total of at least 6200 SRs will be selected from PubMed and assessed for eligibility.

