***Statistical methods:***

Data will be analysed descriptively, using frequencies and proportions for categorical and means with standard deviations (SDs) as well as medians with interquartile ranges (IQRs) for continuous variables. All p-values less than 0.05 will be considered statistically significant. All statistical analyses will be conducted with SAS.

*Table 1. Variable, Measures, and Methods of Analysis*

Variable/Outcome	Outcome measure	Methods of analysis
Primary: Trial participation	Proportion (percentage) of participants who continued to participate after reading the abstract	Chi-square test
Secondary: Informativeness	Likert scale 1 to 4, dichotomized as informative and non-informative	Chi-square test
Secondary: Accuracy	Likert scale 1 to 4, dichotomized as accurate and non-accurate	Chi-square test
Secondary: Attractiveness	Likert scale 1 to 4, dichotomized as attractive and non-attractive	Chi-square test
Secondary: Conciseness	Likert scale 1 to 4, dichotomized as concise and non-concise	Chi-square test
Secondary: Time needed to read the abstract	Time spent on the first page that presents the abstract	Mann-Whitney U-Test

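### The four abstract ratings exist only for readers who clicked Continue, which is the primary outcome; the plan should label these comparisons as conditional and add one supportive sensitivity analysis

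*Combined protocol and SAP*

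**What the plan says.** The Objective section sets the secondary aim: "The secondary objective will be to assess the perception of an abstract based on the four indicators of a well-written abstract". It does not say whose perception is meant, whether everyone shown the abstract or only those who go on.

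Under Intervention, the email link opens the survey tool, where the abstract is shown. "After reading the abstract, participants must actively click the" Continue button to go further. Under Secondary outcomes, that click is what takes the participant into the survey. On the ratings the same section says: "The extent to which participants perceive these criteria to be fulfilled will be quantified on a 4-point Likert scale". Each item is then split into favourable and unfavourable. The analysis table under Statistical methods gives each of the four a plain chi-square test.

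The primary outcome is continuing past the abstract. Its numerator is also described as "the number of participants who read the abstract and proceeded to complete the survey", divided "by the total number of individuals who clicked on the link in the email". Whether the numerator means clicking Continue or finishing the survey, nobody can supply a rating without first clicking Continue.

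No section names the analysis set for the ratings, describes them as conditional on continuing, says how a skipped item is handled, or plans a sensitivity analysis.

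Reading time is defined in two ways. Secondary outcomes has "The time interval is defined as the period between the participant clicking on the link in the email and clicking on the" Continue button; the analysis table has "Time spent on the first page that presents the abstract".

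**The concern.** Randomisation balances the people who are sent each abstract. It does not balance those who remain after a decision that the abstract itself may influence. Here that decision is the endpoint on which the trial is powered to find a difference.

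If readers who dislike an abstract are more likely to leave, the raters are more favourable than all readers, and more so in the arm that loses more people. Two abstracts that are perceived identically could then receive different ratings. Read as written, with a 0.05 threshold and no qualification, the result would look like a randomised effect of abstract length on perception. The four ratings make up the whole of the stated secondary objective, so that conclusion is what is at stake.

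**Working it through.** **Inputs from the plan (Sample size).** Participation 80% vs 68%, two-sided 5% level, 90% power, 279 per group. The documents do not say which abstract is the control, so the arms are not labelled short or long here.

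**Reproducing the plan's figure.** With pooled variance and no continuity correction:

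n = [1.960·√(2·0.74·0.26) + 1.2816·√(0.80·0.20 + 0.68·0.32)]² / 0.12² = (1.960·0.6203 + 1.2816·0.6145)² / 0.0144 = 278.7, so 279 per group. This matches.

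**Who can rate.** 279·0.80 = 223 and 279·0.68 = 190. About 56 and 89 readers (20% and 32%) leave without a rating.

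**Assumptions, not in the documents.** A share f = 60% of all link-openers hold a favourable opinion in both arms, so every rejection is false. The odds ratio (OR) for continuing, favourable versus unfavourable readers, is the same in both arms.

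**Formulas.** Let c be the share continuing, r the favourable share among raters and l the favourable share among leavers. Then c·r + (1−c)·l = f, and OR = [r/(1−r)] / [l/(1−l)]. Solve for r in each arm. With d the gap between the arms in r, s₀ the pooled standard error and s₁ the unpooled one, the rejection rate is Φ[(d − 1.96·s₀)/s₁] + Φ[(−d − 1.96·s₀)/s₁].

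**One case in full: OR 2, 80% vs 68%.**
- In the 80% arm r = 63.4% and l = 46.4%; check 0.80·0.634 + 0.20·0.464 = 0.600.
- In the 68% arm r = 65.4% and l = 48.6%; check 0.68·0.654 + 0.32·0.486 = 0.600.
- The spurious gap is d = 2.0 points, and s₀ ≈ s₁ ≈ 0.0473.
- Rejection ≈ 7.0%.

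| OR, both arms | Raters favourable, 80% vs 68% | False rejection | Raters favourable, 80% vs 74% | False rejection |
|---|---|---|---|---|
| 1 | 60.0 vs 60.0 | 5.0% | 60.0 vs 60.0 | 5.0% |
| 2 | 63.4 vs 65.4 | 7.0% | 63.4 vs 64.4 | 5.5% |
| 3 | 65.3 vs 68.5 | 10.2% | 65.3 vs 66.9 | 6.4% |
| 5 | 67.6 vs 72.2 | 16.9% | 67.6 vs 69.9 | 8.0% |

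The assumed 60% matters little. At 80% vs 68%, ORs of 2, 3 and 5 give 7.0%, 10.2% and 16.4% if 50% are favourable overall, and 6.8%, 9.7% and 15.6% if 70% are.

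**Width of trimming (Lee) bounds.** The share trimmed from the better-retained arm is (0.80 − 0.68)/0.80 = 15%. If that arm's raters are favourable in proportion p, between 15% and 85%, the trimmed value runs from (p − 0.15)/0.85 to p/0.85. The width is 0.15/0.85 = 17.6 points. At 80% vs 74% the trim is 7.5% and the width 0.075/0.925 = 8.1 points.

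**Width of best/worst-case bounds over all link-openers.** With an assumed 70% favourable among raters in both arms, the 80% arm lies between 56.0% and 76.0% and the 68% arm between 47.6% and 79.6%. The difference runs from −23.6 to +28.4 points, a width of 20 + 32 = 52 points.

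**The case against.** The strongest reply is that the limit is plain from the design. Someone who closes the abstract page cannot be asked about it. Attrition by arm is measured and tested as the main result, and the secondary objective never claims to cover every link-opener. Selection may also be weak: authors from any field are shown an untitled urology abstract, and many may leave for lack of interest in the topic rather than from a view of the writing. Much of this stands. It is why the effect is put as small for modest associations and why the ratings need no redesign. It does not remove the need to say in the plan what the tests compare.

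A reader might go further and infer that the rating tests are badly biased. Larger figures can be produced. If leavers in both arms are 40%, 30% or 20% favourable, false rejection at 80% vs 68% is 16%, 31% or 53%. Those rows need ORs of 2.8–3.4, 4.9–6.7 and 9.3–14.9, and nothing in the documents points to associations at the upper end.

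A reader might also point to a relation between opinion and leaving in one arm only. With 74% continuing in both arms, that gives 15%, 31% or 56% rejection at ORs of 2, 3 and 5. It cannot be used to argue for trimming bounds. Those bounds target people who would continue with either abstract and assume that nobody continues only for the abstract with lower continuation. With equal continuation, that assumption makes the continuers the same people in both arms. The scenario therefore either breaks the assumption or shows a real difference among continuers.

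The choice between trimming bounds and best/worst-case bounds is a matter of judgement; either will do. The two reading-time definitions describe nearly the same interval, because the link opens on the abstract page, so that point is minor.

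**Conclusion.** The concern holds in a limited form. As written, the plan tests perception in a subset defined by its own primary outcome, without saying so, and a selection artefact could be reported as a randomised effect. The size depends on a link between opinion and leaving that the trial cannot observe. Under the stated assumptions, false rejection is 7% to 17% for ORs of 2 to 5 at the design difference, 6% to 8% if continuation differs by only 6 points, and 5% if leaving is unrelated to opinion.

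A reader might infer that the primary result or the sample size is affected. Neither is: the primary comparison uses all link-openers as denominator, and 279 per group reproduces. This is a change that should be made to secondary outcomes, with medium confidence, since the direction and size of any bias cannot be known from the documents.

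**What to change.** In Secondary outcomes and Statistical methods:

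- State that the rating comparisons are among continuers, are conditional on the primary outcome, and will not be concluded as randomised effects on all readers. Interpret them alongside the primary result.
- For each item, report the number rated over link-openers by arm, so that continuers who skip an item are visible too.
- Prespecify one supportive sensitivity analysis, not a gate on claims. Trimming (Lee) bounds with 95% confidence limits are one option; state their target (people who would continue with either abstract) and their monotone-continuation assumption. Best/worst-case bounds over all link-openers are an acceptable alternative.
- If the proportion who continued and rated favourably is shown over all link-openers, keep it descriptive, because it mixes continuing with perception. With identical 75% ratings it would be 0.80·0.75 = 60% vs 0.68·0.75 = 51%, significant 57% of the time.
- Minor: reconcile the two reading-time definitions. If the interval ends at the Continue click, label that Mann-Whitney test as conditional on continuing as well.

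The cost is some wording and a few extra tables, with no new data and no more participants. The drawback is that the bounds are wide when continuation differs (before sampling error, 17.6 points for trimming bounds at the design rates), so they will often be uninformative. That is a reason to keep them supportive.

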**Additional outcomes:**

In addition, data on some formal and structural characteristics of an Abstract (structure, length, funding, and registration) as well as participant characteristics (age, gender, country, and experience in writing SRs) will be collected.

**Sample size:**

Assuming an 80% trial participation in the control group, a two-sided significance level of 5% ( $\alpha = 0.05$ ), and a power of 90% ( $\beta=10\%$ ), 558 participants (279 per group) are needed to detect a relative difference in trial participation of 15% (80% vs. 68%). The sample size calculation was carried out using the PROC POWER function in SAS. Given an expected response of 9.6%, the sample size was estimated to be 5813. Additionally, expecting an approximately 5% exclusion due to study types other than SR^13 or duplicate email addresses, the sample size was increased to 6103. To achieve this, a total of at least 6200 SRs will be selected from PubMed and assessed for eligibility.

**Recruitment and incentives**

The corresponding authors of the identified SRs will be contacted by email with a link to the survey and invited to participate. To achieve the highest possible response, recruitment will follow the recommendations for increasing the response of electronic questionnaires from Edwards et al..

Accordingly, we will:

- use a short and personalized cover letter that includes a picture
- use a simple but meaningful header, not including the term “survey”
- use a brief e-questionnaire that is designed in an attractive way
- give participants enough time, but also set and communicate a firm deadline.
- send the email by a female investigator.

The initial email invitation to participate in the study will be sent in August 2024. After two weeks, a first reminder will be sent out. A second reminder will be sent after four weeks. Data collection will conclude eight weeks after the initial e-mail has been sent.

No financial incentives are planned.

**Participant timeline**

[figure not shown]

Figure 1. Flowchart: Preparation for enrollment and recruitment

**Allocation:**

**Sequence generation and implementation:**

In a 1:1 ratio, the corresponding authors will be randomly assigned to either the group receiving the long abstract or the group receiving the short abstract using the PROC PLAN procedure in SAS.

***Blinding:***

The participants will be blinded to the intervention. In the cover letter, participants will be informed that the study aims to examine the characteristics of an abstract. However, they will not be informed that the primary focus of this study is the influence of the abstract's length. Furthermore, the participants will be not aware of the number of different abstracts that were randomly allocated.

***Data collection and management:***

All data will be collected and managed using the online survey tool SoSci Survey.

***Statistical methods:***

Data will be analysed descriptively, using frequencies and proportions for categorical and means with standard deviations (SDs) as well as medians with interquartile ranges (IQRs) for continuous variables. All p-values less than 0.05 will be considered statistically significant. All statistical analyses will be conducted with SAS.

*Table 1. Variable, Measures, and Methods of Analysis*

Variable/Outcome	Outcome measure	Methods of analysis
Primary: Trial participation	Proportion (percentage) of participants who continued to participate after reading the abstract	Chi-square test
Secondary: Informativeness	Likert scale 1 to 4, dichotomized as informative and non-informative	Chi-square test
Secondary: Accuracy	Likert scale 1 to 4, dichotomized as accurate and non-accurate	Chi-square test
Secondary: Attractiveness	Likert scale 1 to 4, dichotomized as attractive and non-attractive	Chi-square test
Secondary: Conciseness	Likert scale 1 to 4, dichotomized as concise and non-concise	Chi-square test
Secondary: Time needed to read the abstract	Time spent on the first page that presents the abstract	Mann-Whitney U-Test

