**Study design:**

This will be a two-arm, single-blinded, superiority, parallel-group randomized controlled trial (RCT) with 1:1 allocation of intervention and control groups.

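### All six tests, four of them serving one secondary objective, are declared significant at an unadjusted p<0.05, with no statement that the secondary results are exploratory

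*Combined protocol and SAP*

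**What the plan says.** The decision rule under Statistical methods is one sentence: "All p-values less than 0.05 will be considered statistically significant". The table that follows lists six between-arm tests: a chi-square test for trial participation (primary), a chi-square test for each of four dichotomised ratings, and a Mann-Whitney U test for reading time. The rule covers all six.

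The secondary objective ties the four ratings together as indicators of good abstract writing: "These indicators state that abstracts should be: a) informative, b) accurate, c) attractive, and d) concise". The Secondary outcomes section presents them in the same way. Reading time is added there as a separate secondary outcome and is not one of the four indicators.

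The Sample size section uses "a two-sided significance level of 5" per cent, for trial participation only. No section adjusts the secondary tests, tests them in a fixed order, or calls them exploratory. The section does open by saying that the data will be analysed descriptively, but the significance rule and a table with a hypothesis test for every outcome follow.

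**The concern.** The plan does more than leave multiplicity unmentioned. It gives an explicit rule which, followed exactly, produces unadjusted declarations of significance on every secondary outcome. Four of those declarations answer one question, how the abstract is perceived, and the plan has neither a composite rating nor a rule for how many ratings must differ. Each rating is therefore a separate opportunity, in either direction, to report a significant perception difference between the long and the short abstract.

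At stake is the strength of the secondary conclusions. A single significant rating out of four is weaker evidence than its own p-value suggests, and nothing in the plan tells the reader to treat it with more caution than the primary result.

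**Working it through.** **Inputs from the documents.** Threshold 0.05 for every p-value (Statistical methods). Six tests: one primary, four ratings, reading time (table in the same section). Two-sided 5%, 90% power, 80% vs 68% and 279 per group, for the primary outcome (Sample size). Allocation 1:1 (Study design).

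**Inputs that are assumptions.** The correlation between the four test statistics, taken as equal for all pairs. The true rating proportions. The number of raters per arm.

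**1. The plan's own figure.** With pooled variance, no continuity correction and mean proportion (0.80 + 0.68)/2 = 0.74:

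n = [1.960 × √(2 × 0.74 × 0.26) + 1.282 × √(0.80 × 0.20 + 0.68 × 0.32)]² / 0.12² = 278.7, so 279 per group.

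This matches. The 5% in that calculation belongs to one test, and that test keeps its 5% whatever is done with the secondary outcomes.

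**2. Four ratings, none truly different, independent statistics.**

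1 − 0.95⁴ = 0.185, which is 3.7 times the per-test level.

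**3. The same, with correlated statistics.** Simulating 2,000,000 sets of four equally correlated normal statistics, and counting sets in which at least one exceeds 1.96 in absolute value, gives:

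| Correlation | At least one p<0.05 | Multiple of 5% |
|---|---|---|
| 0 | 18.6% (exact 18.5%) | 3.7 |
| 0.3 | 17.4% | 3.5 |
| 0.5 | 15.6% | 3.1 |
| 0.7 | 13.0% | 2.6 |
| 0.9 | 9.4% | 1.9 |

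A second simulation (20,000 trials per setting) dichotomised correlated ratings, with 223 and 190 raters and 60% or 80% favourable. It gave about 17–18% at a latent correlation of 0.5, 16% at 0.7 and 13% at 0.9. These values are higher than in the table because dichotomising weakens the correlation between ratings.

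**4. If conciseness truly differs.** Three true nulls remain: 1 − 0.95³ = 0.143 if independent, and less under positive correlation.

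**5. Price of adjusting the four ratings by Holm.** Suppose everyone who continues also rates: 279 × 0.80 = 223 and 279 × 0.68 = 190 raters. Borrow 80% vs 68% as the true difference on a rating; the documents give no rating proportions.

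- Pooled proportion: (223 × 0.80 + 190 × 0.68)/413 = 0.745.
- Standard error under no difference: √(0.745 × 0.255 × (1/223 + 1/190)) = 0.0430.
- Standard error under the difference: √(0.16/223 + 0.2176/190) = 0.0432.
- Power at 0.05: Φ((0.12 − 1.960 × 0.0430)/0.0432) = about 0.80.
- Power at 0.05/4 = 0.0125: Φ((0.12 − 2.498 × 0.0430)/0.0432) = about 0.61.

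The last line approximates Holm when only one rating truly differs. If all four differ, simulation at correlations of 0.3 to 0.5 gives about 0.70–0.71 per rating.

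**The case against.** The case for leaving the rule alone has real substance.

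- **The hierarchy is visible.** One outcome is named primary and only that one is powered. With a single pre-specified primary outcome, many statisticians leave secondary outcomes unadjusted. This stands as an argument against compulsory adjustment. It does not justify calling primary and secondary results significant by the same rule.
- **No 5% promise is broken.** A reader might infer that the plan exceeds an error rate that it set for itself. It does not: 0.05 is a per-test threshold and the alpha of the primary comparison. No family-wise rate is stated for the secondary outcomes.
- **The multiplier is not fixed.** A reader might infer that false claims are three to four times as likely as 5%. That holds only up to a correlation of about 0.55. Four ratings of one abstract by the same person are likely to be positively correlated, and strong correlation brings the multiple below three.
- **No rule says which abstract is better written.** A reader might infer that any one significant rating would win that claim, or become the trial's headline. The plan analyses four named criteria separately and sets no such rule, and nothing in the documents supports a prediction about the headline.
- **The global null is doubtful.** With 771 against 277 words, a true difference in conciseness is plausible, and equal reading times are hard to credit. Figures for five or six independent tests (1 − 0.95⁵ = 22.6%, 1 − 0.95⁶ = 26.5%) therefore say little here. The second also includes the primary test, whose error is unaffected. The 14% bound for three ratings answers the point about conciseness.

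**Conclusion.** The point holds as a modest one about the secondary outcomes. The plan declares all six tests significant at an unadjusted 0.05 and does not mark the secondary ones as exploratory. For the four ratings, with no true difference on any, the chance of at least one significant result is about 19% under independence, 16% at correlation 0.5, 13% at 0.7 and 9% at 0.9, against 5% per test. If conciseness truly differs, it is at most about 14% for the other three under independence or positive correlation.

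The direction is secure, since there was inflation at every correlation examined. Its size depends on a correlation that the documents do not give. The primary test, its 5% level and the sample size are not affected. The change is worth making because it is cheap and fixes, before the data are seen, what the secondary results can support.

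**What to change.** Replace the significance sentence under Statistical methods with:

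'Only the primary chi-square test is confirmatory, at two-sided 5%. All secondary results, including the four ratings and reading time, are exploratory; they are reported as effect estimates with 95% confidence intervals and unadjusted p-values, and are not called statistically significant.'

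The tests in the table can stay. The cost is some wording and a few extra lines of output, and the authors give up any confirmatory claim on a secondary outcome. Design, primary analysis and sample size do not change.

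If the authors want significance claims on the ratings, they should specify Holm at 5% overall across those four, so that the smallest of the four p-values must reach 0.0125. Reading time lies outside that family. The price is lower power per rating: from about 80% to about 61% when one rating truly differs, under the borrowed 80% vs 68% and 223 and 190 raters. Either choice should be recorded before the data are analysed.
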